5.2 Dose Modifying Toxicities (DMT)

Toxicities will be graded according to CTCAE version 5.0 of the NCI Common Terminology Criteria for Adverse Events. CTCAE version 5.00 is identified and located on the CTEP website at http://ctep.cancer.gov/protocolDevelopment/electronic_applications/ctc.htm. All appropriate treatment areas should have access to a copy of CTCAE version 5.0.

DMT will be defined as any of the events listed in this section that are at least possibly related to the investigational agent that occur regardless of expectedness. Please consult Table 7 for appropriate dose modifications.

- 5.2.1 The following are Dose-Modifying Toxicities (DMT's)
 - Any selumetinib-related adverse event that results in a delay of treatment > 7 days
 - Non-hematologic dose modifying toxicity is defined as:
 - o Any grade 4 non hematologic toxicity
 - o Any grade 3 non-hematologic toxicity with the exception of:
 - Grade 3 nausea and vomiting of < 3 days
 - Grade 3 asymptomatic elevation of transaminases that returns to levels meeting eligibility criteria within 7 days of study drug interruption and does not recur upon restarting drug
 - Grade 3 fever or infection if fewer than 3 days in duration
 - Grade 3 asymptomatic hypophosphatemia, hypokalemia, hypocalcemia or hypomagnesemia responsive to oral supplementation

- Grade 3 asymptomatic elevation of CPK
- Any grade 2 non-hematological toxicity that persists for more than 7 days and is considered sufficiently medically significant or sufficiently intolerable by patients as to warrant treatment interruption and/or dose reduction will be considered dose-modifying.
- Hematologic dose modifying toxicity is defined as:
 - o Any grade 4 hematologic toxicity with the exception of lymphopenia
 - o Grade 3 thrombocytopenia with bleeding

5.3 Criteria for starting subsequent courses

A course may be repeated every 28 days if the patient has at least stable disease and the patient meets the following criteria within seven days of the start of each course:

- ANC $\geq 1,000/\mu L$
- Platelets $\geq 100,000/\mu L$
- Non-hematologic dose modifying toxicity related to selumetinib recovered to < grade 2 or baseline (for rash or diarrhea: tolerable grade 2 or baseline)
- No evidence of progressive disease

5.4 Concomitant Medications and Supportive Care Guidelines

Because there is a potential for interaction of selumetinib with other concomitantly administered drugs through the cytochrome P450 system, the case report form (CRF) must capture the concurrent use of all other drugs, over-the-counter medications, or alternative therapies. Refer to APPENDIX C for a list of medications which should be avoided, if possible. The Principal Investigator should be alerted if the patient is taking any agent known to affect or with the potential to affect selected CYP450 isoenzymes. Data to be recorded for each medication in CRF is Indication, Drug Name, Dose, Start and Stop dates

[figure not shown]
Unless considered clinically indicated, patients should avoid taking other additional non-study medications that may interfere with the study medications. In particular, patients should avoid medications that are strong inhibitors or moderate/strong inducers of CYP3A4 and fluconazole (potent CYP2C19 and moderate CYP3A4 inhibitor), as this may interfere with the metabolism of selumetinib.

High vitamin E doses may potentiate warfarin's anticoagulant activity. Monitor PT/INR more frequently in patients receiving both warfarin and selumetinib hydrogen sulfate capsules. As selumetinib capsules contain vitamin E, patients should not take any supplemental vitamin E during treatment with selumetinib.

- 5.4.1 Follow up for certain adverse events should be performed to better characterize the effects of selumetinib therapy
 - **Peripheral Edema** Patients experiencing grade 3 or prolonged grade 2 (> 14 days) edema should have cardiac ejection fraction (EF) measurements, serum chemistry (including electrolytes and albumin), and routine urinalysis as clinically indicated.

- Cardiac monitoring Reversible, asymptomatic reductions in LVEF have been recorded in a small number of patients receiving selumetinib in studies with scheduled echocardiography assessments. Guidance for the investigation and management of decreases of LVEF is described below.
 - o ECHO Patients will have increased monitoring for cardiac function (ECHO) at baseline and every 3 months thereafter during treatment. Patients who develop symptoms consistent with cardiac impairment (e.g., congestive cardiac failure, pulmonary edema, or dyspnea) at any time during treatment should have EF measurements (echocardiography) at the time of the event as well as other routine investigations. Patients who show a ≥10% change in ejection fraction from baseline should be managed according to the recommended management for cardiac adverse events described below and in Table 7. Patients who have a drop in LVEF of ≥10% from baseline and to below 55% at the discontinuation of selumetinib, should have a follow-up ECHO after 30 days to evaluate the potential for reversibility.

Management of Asymptomatic Left Ventricular Ejection Fraction (LVEF) Reduction

[figure not shown]

- **Muscle weakness** Patients should be monitored for CPK elevation and for the development of muscle weakness (refer to management guidelines described in Table 7).
- Respiratory events (including dyspnea or pulmonary edema) should be followed up with a chest X-ray (PA and lateral view). See below algorithm for management.

[figure not shown]
Guidance for management of patients with dyspnoea*

* Not considered related to disease under study

† Includes selumetinib/placebo or combination treatment, as appropriate

- Oxygen saturation will be measured at baseline and again following any respiratory event.
- Visual disturbances Patients experiencing visual disturbances should undergo a complete ophthalmologic examination which includes the following:
 - Visual acuity
 - Visual fields, if feasible
 - o Fundoscopic exam
 - See Table 7 and algorithm below

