Scheduled on-treatment assessments (Week 4 or 8) of LVEF were included in two studies of selumetinib monotherapy to evaluate a possible cardiac etiology for peripheral edema. Small median reductions (<10 percentage points) from baseline were recorded during selumetinib treatment in both studies, although individual patient changes were highly variable (−25 to +19 percentage points). No comparative data are available from these studies. Clinically meaningful reductions in LVEF (≥10 percentage points and to below 55%) in patients receiving selumetinib in combination with chemotherapy have been recorded in two randomized double-blind placebo-

controlled Phase 2 studies with scheduled Week 6 echocardiography assessments (D1532C00006 and D1532C00016). These asymptomatic reductions occurred in 13.6% vs. 7.1% of patients with NSCLC receiving selumetinib or placebo in combination with docetaxel and in 20.5% vs. 11.4% of patients with advanced melanoma receiving selumetinib or placebo in combination with dacarbazine. Evidence of reversibility of LVEF changes on continuing selumetinib (often without therapeutic treatment) has been demonstrated in patients with follow-up assessments available.

Increase in Creatinine Phosphokinase Levels

Increased CPK levels have been reported with MEK inhibitors ³⁸⁻⁴⁰, which may suggest a class effect. Scheduled measurement of CPK levels has not been included in studies of selumetinib. However, AEs of increased CPK levels have been reported in a small number of patients. In study D1532C00006, CPK levels were measured at a single investigational site in patients with melanoma believed by the investigator to be receiving selumetinib + dacarbazine. AEs of increased CPK levels were reported in 7 patients (15.9% of the overall selumetinib + dacarbazine group). CPK levels were not measured in the 3 patients at the same site who received placebo + dacarbazine. A causal relationship between selumetinib and increased CPK levels has not been established.

Muscle Weakness

Neck extensor muscle weakness (with mild increase in CPK levels), reversible on selumetinib interruption, has been reported in 3 patients with uveal melanoma treated with selumetinib in a non-AZ-sponsored study.⁴¹ A relationship between selumetinib and muscle weakness has not been established.

Potential Drug Interactions

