5.5 Duration of Therapy

In the absence of treatment delays due to adverse event(s) or disease progression, treatment may continue for 26 courses (approximately two years) or until one of the Off Treatment Criteria found

in Section 5.6 applies.

During the second year of treatment, procedures consistent with good clinical care will continue. Patients will be seen monthly for medical history, physical exam (including height, weight, vital signs, and performance status), neurologic exam, dates of drug administration, relevant laboratory evaluations and routine neuro-imaging assessments. Therapy-related events will be recorded per standard assessments, including adverse events, date of disease progression, date of last follow up, date patient goes off treatment and date off study. Please review the table in Section 10 of the protocol for the required assessments and intervals. All patients must discontinue treatment with selumetinib following the completion of 26 courses of treatment.

5.6 **Duration of Follow Up**

Discontinuation of Treatment

At the discontinuation of treatment, the "Off Treatment Date" is to be recorded in the CRF and is to be consistent with the reason given for going off treatment. The "Last Treatment Date" is defined as the last date that the patient received protocol based therapy. Date of "off treatment" must be the greatest of the date of last treatment, date of procedure, date of patient assessment, notification of patient/family decision, or decision made by the physician that resulted in the patient being taken off protocol treatment. The reason for discontinuation of treatment must be documented by the attending investigator in the medical record and recorded in the CRF. The "Off Treatment Date" and the "Last Treatment Date" should be the same for patients that complete all protocol defined treatment.

Patients will be considered Off Treatment for the following reasons:

- 5.6.1 Development of unacceptable toxicity as outlined in Section 5.2.1 that does not resolve within 14 days.
- 5.6.2 Non-compliance with study guidelines
- 5.6.3 Progressive disease, as outlined in section 11.1 and 11.2
- 5.6.4 Development of a medical or psychiatric illness, that in the investigator's judgment renders the patient incapable of further therapy on this protocol
- 5.6.5 The patient, parent or legal guardian refuses further treatment on this protocol
- 5.6.6 Pregnancy
- 5.6.7 Completion of maximum number of courses of treatment with selumetinib

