10 STUDY CALENDAR

	Pre- therapy	Courses 1-12 ^H	Courses 13-26 ^H	Completion/ Discontinuation Of Treatment
PHYSICAL ASSESSMENTS				Ì
Medical history	X	X ^A	X	X
Physical exam /height/weight	X	X ^A	X	X
Vital signs	X	X ^A	X	X
Performance status	X	X^{A}	X	X
Neurologic exam	X	X ^A	X	X
Smoking Status	X			
Hearing evaluation (stratum 1)#	X	X ^C	X^{C}	
LABORATORY EVALUATIONS				
CBC - WBC, HgB, Hct, Platelets, ANC, ALC B	X	X ^A	X^{A}	X
PT and INR for those patients on warfain		X	X	
Serum Chemistry - Sodium, Potassium, Bicarbonate, Chloride, Calcium, BUN, Creatinine, Glucose, Phosphorous, Magnesium, Albumin, Total Protein ^B	X	X ^A	X^{A}	X
SGPT (ALT), SGOT(AST), Alkaline phosphatase, Total Bilirubin ^B	X	X ^A	X^{A}	X
CPK **	X	X ^A	X^{A}	
Serum or urine pregnancy test (for females of childbearing potential)	X	X ^A	X ^A	
Echocardiogram (ECHO)	X	X ^C	X^{C}	
12-lead EKG	X			
Ophthalmology evaluation	x D	x ^D	x ^D	X
Pulse Oximetry	X			
Chest X Ray	\mathbf{X}^{E}			
Growth plate assessment	X	X ^C	X ^C	
IMAGING ASSESSMENTS				
Brain MRI	X	X ^C	X ^C	X
Spine MRI	X	X ^{C, F}	$X^{C, F}$	X F
CORRELATIVE STUDIES				
NF1-QOL	X	Every 3 courses	Every 4 courses	
Pre-trial tumor materials (if available)	X			

	Pre- therapy	Courses 1-12 ^H	Courses 13-26 ^H	Completion/ Discontinuation Of Treatment
--	-----------------	------------------------------	-------------------------------	--

- A. To be done prior to each course. See Section 5.3. Height does not need to be recorded for patients >18 years of age after initial measurement. Childbearing potential are those female patients who have reached menarche.
 - # Audiology will include measurement of pure tone thresholds and determination of word recognition scores
- B. To be done more frequently throughout the duration of treatment if required to monitor toxicities.
- C. To be done prior to initiation of therapy, after courses 3, 6, 9, 12, 16, 20, 26 until progression or end of therapy. The assessment is a tibial x-ray (AP and lateral views) of the right knee. If abnormalities are detected on routine X-rays, MRI scan of both knees should be performed. Growth plate assessments should be done for patients under the age of 18 only, unless growth plate closure is documented.
- D. Baseline and following any visual disturbance during treatment. See section 5.2
- E. To be done if pulse oximetry is < 95% or if clinically indicated during treatment. See section 5.2

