- F. MRI Spine should be done at the same time points as the standard MRI brain, if clinically indicated.
- G. Formalin fixed paraffin embedded tumor tissue will be collected from all patients who have pre-trial tumor material available
- H. All evaluations to be completed within 7 days of anticipated start date of the next course.

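### Section 5.4.1 requires an ECHO every 3 months throughout treatment, but the study calendar spaces the second-year ECHOs 16, 16 and 24 weeks apart

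*Combined protocol and SAP*

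**What the plan says.** Three current parts of the protocol bear on the timing of the ECHO.

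- Section 5.4.1, under cardiac monitoring: "Patients will have increased monitoring for cardiac function (ECHO) at baseline and every 3 months thereafter during treatment". The rule covers the whole of treatment, which section 5.5 allows to run for 26 courses.
- Section 10, study calendar: the ECHO row carries footnote C in both the courses 1-12 and the courses 13-26 columns. Footnote C reads: "To be done prior to initiation of therapy, after courses 3, 6, 9, 12, 16, 20, 26 until progression or end of therapy". The same footnote serves the hearing, growth plate and MRI rows.
- Section 5.5, in its paragraph on the second year of treatment: "Please review the table in Section 10 of the protocol for the required assessments and intervals".

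Footnote H adds a visit window: "All evaluations to be completed within 7 days of anticipated start date of the next course". No text states whether section 5.4.1 or the calendar governs where they differ.

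**The concern.** The two schedules agree, nominally, up to course 12 and part company after it. Staff who do what section 5.5 tells them, and take second-year intervals from the calendar, will miss the interval that 5.4.1 states. This affects every patient who goes far enough into the second year.

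At stake is the detection of falls in LVEF. Section 5.4.1 acts on a change in ejection fraction of 10% or more from baseline, and that change has to be measured before it can be acted on. Sections 2.2.2 and 5.4.1 describe the reductions seen so far as asymptomatic. The extra ejection fraction tests that 5.4.1 triggers for cardiac symptoms or marked edema therefore cannot be relied on to find such falls between scheduled ECHOs.

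**Working it through.** **Inputs**

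- Course length is 28 days (Schema), with courses back to back and no planned break (5.1), for up to 26 courses (5.5).
- The ECHO interval is 3 months (5.4.1). Taking a month as 30.4375 days, 3 × 30.4375 = 91.3 days, and 91.3 / 7 = 13.04 weeks.
- Scheduled ECHOs fall before therapy and after courses 3, 6, 9, 12, 16, 20 and 26 (section 10, footnote C).
- The visit window is 7 days (section 10, footnote H).

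**Step 1: the plan's own time base.** 26 × 28 = 728 days, and 728 / 365.25 = 1.99 years. This reproduces the approximately two years given in 5.5.

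**Step 2: nominal gaps.** Gap = difference in course number × 28 days.

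| Between ECHOs | Days | Weeks | Days beyond 91.3 |
|---|---|---|---|
| 0-3, 3-6, 6-9, 9-12 (each) | 84 | 12 | none |
| 12-16 | 112 | 16 | 20.7 |
| 16-20 | 112 | 16 | 20.7 |
| 20-26 | 168 | 24 | 76.7 |

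These assume no treatment delays. Delays between courses would lengthen the gaps.

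**Step 3: can the visit window close them?** The smallest gap the window allows is the nominal gap less 7 days at each end. For the 16-week gaps, 112 − 14 = 98 days (14 weeks). For the last, 168 − 14 = 154 days (22 weeks). All three still exceed 91.3 days.

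**Step 4: dates side by side.** The course-12 ECHO is at week 12 × 4 = 48. Stepping on by 13.04 weeks, 5.4.1 makes ECHOs due at weeks 61, 74, 87 and 100, all before treatment ends at week 104. The calendar gives weeks 64, 80 and 104.

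**Step 5: time outside the stated interval.** The unrounded excesses sum to 118.1 days. Courses 13 to 26 last 14 × 28 = 392 days, and 118.1 / 392 = 30%. This describes the schedule for a patient who completes all 26 courses on time. It is not a measure of risk.

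**The case against.** The best defence is that the step-down is deliberate and the calendar governs. Section 5.5 names the calendar as the place to find second-year intervals, its own list of second-year procedures does not mention ECHO, and 5.4 is headed as supportive care guidance. The calendar also relaxes quality of life in the second year, to "Every 4 courses". On this reading 5.4.1 is simply not updated. That may be so, but it does not remove the conflict: 5.4.1 contains no second-year exception, and one of the two texts still has to change. Nor does a 4-course step-down explain the last gap of 6 courses. Section 9.1.3 gives the same course list for MRI, so the ECHO row may have inherited an imaging schedule; that is inference.

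A second defence is that the total count is about right. Counted strictly from the start of treatment, 728 / 91.3 = 7.97, so seven ECHOs fall due on treatment and the eighth at day 730.5, just after the end. The calendar also has seven. This stands, and it shows that the fault is one of spacing.

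Third, the contrast between the two years is less clean than the nominal gaps suggest. If the baseline ECHO is treated as a non-imaging eligibility evaluation, sections 3.4.1 and 3.4.2 let it be up to 14 + 14 = 28 days old at the first dose. The first interval could then be 84 + 28 = 112 days. The 7-day window could also stretch a later first-year gap to 84 + 14 = 98 days. A reader might infer that the first year always meets the 3-month rule; the documents support only the nominal 12 weeks.

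Fourth, consequence. A reader might infer that falls in LVEF will go unseen and do harm in the second year. The documents do not support that step. The quoted excesses, such as "13.6% vs. 7.1% of patients with NSCLC receiving selumetinib or placebo in combination with docetaxel", come from week-6 assessments in combination with chemotherapy. Section 7 lists reduced LVEF as rare (<3%), and section 2.2.2 adds: "Evidence of reversibility of LVEF changes on continuing selumetinib (often without therapeutic treatment) has been demonstrated in patients with follow-up assessments available". No second-year onset rate is given.

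Finally, a reader might infer a further gap at discontinuation. The 30-day repeat ECHO is for patients "who have a drop in LVEF of ≥10% from baseline and to below 55% at the discontinuation of selumetinib", yet the calendar marks no ECHO in that column. Completers have the ECHO after course 26, patients who stop for progression at a scheduled visit have one due then, and patients with cardiac symptoms or marked edema are tested when these occur. What remains is a small, unquantified group, and the LVEF algorithm figures in 5.4.1 and 6.2, which were not available for this review, may cover it. The point is not pressed.

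**Conclusion.** The inconsistency is real and should be corrected. After course 12 the calendar's ECHO gaps are nominally 16, 16 and 24 weeks against a stated rule of about 13 weeks, and the visit window does not reconcile them. The longest gap is nearly twice the stated interval and cannot be read as a loose version of 3 months.

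The gap lengths rest on 28-day courses without delay and on a 3-month interval of 91.3 days. Both schedules are legible, current text. The algorithm figures not seen might add cardiac rules, but the two written schedules would still disagree.

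The weight is that of a safety-monitoring rule the protocol contradicts itself on. The Simon two-stage design in 13.2 is untouched: no effect on alpha, power or either primary endpoint. The clinical consequence cannot be sized from the documents.

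**What to change.** Give the ECHO row its own footnote in the section 10 calendar: before therapy, after every 3 courses through course 24, and at completion. Leave footnote C as it is for the other rows. The longest nominal on-treatment gap then becomes 12 weeks, and the last, from course 24 to course 26, is 8 weeks.

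**Cost.** A completer now has ECHOs after courses 3, 6, 9, 12, 16, 20 and 26, which is 7 after baseline. Under the fix these fall after courses 3, 6, 9, 12, 15, 18, 21 and 24 plus completion, which is 9. That is about 2 extra per completer relative to the calendar. Once the course-12 ECHO has been done, the interval in 5.4.1 already calls for four more before the end of treatment, and the completion ECHO is already scheduled after course 26.

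**Alternative.** If the sponsor intends the longer second-year interval, amend 5.4.1 to state it and leave the calendar alone. That costs one sentence and no extra ECHOs, but the sponsor should then say why a 24-week final gap is acceptable.

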5.4.2 Febrile Neutropenia

Febrile neutropenia should be managed according to the local institutional guidelines. Measures include laboratory testing, blood and urine cultures, and institution of broad spectrum antibiotics.

5.4.3 Diarrhea

[figure not shown]
Patients should be advised to drink plenty of water or rehydration fluids to avoid dehydration if diarrhea occurs. Should diarrhea occur follow the loperamide dosing guidelines in Table 6 immediately following first dose of diarrhea. Patients should be given dietary advice in case of diarrhoea (e.g. BRAT [bananas, rice, apple sauce, toast, plain pasta] diet; readily digestible food; avoidance of lactose-containing products, fried, fatty or spicy food) and increase fluid intake. Refer to Table 7, Section 6.2 when modifying the selumetinib dose in response to diarrhea.

Table 6

Weight Specific Guidelines for Therapeutic Use of Loperamide				
Weight	Initial (Loading) Loperamide dose	Subsequent daytime loperamide	Subsequent nighttime loperamide	
(kg)	(mg)	dose	dose	
8-10	1	0.5mg q 3h	0.75mg q 4h	
10-20	1	1mg q 3h	1mg q 4h	
20-30	2	1mg q 3h	2mg q 4h	
30-42	2	1mg q 2h	2mg q4h	
> 42	4	2mg q 2h	4mg q 4h	

Please see algorithm below when assessing diarrhea:

Guidance for the management of patients with diarrhea Diarrhea CTC Grade 1 or 2 CTC Grade 1 or 2 complicated diarrhea* and uncomplicated diarrhea CTC Grade 3 or 4 at any time Hospitalization Loperamide : 4mg initially Treat as per local practices then 2mg every 4 hours or after each unformed stool antibiotics). Dietary management Selumetinib dose interruption

^{*}Diarrhea becomes complicated by associated vomiting or inability to take oral fluids; marked abdominal distension or cramping; bloody stools, fever or symptoms of hypotension

If Grade 1/2 diarrhea: Full clinical and laboratory evaluation including ruling out infectious causes (Clostridium difficile or viral causes).

If Grade 3/4 diarrhea: Consider hospitalization if needed, full clinical and laboratory evaluation

including infectious evaluation. Consider starting octreotide. Hold selumetinib until < tolerable grade 2. Continue loperamide.

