3.1.3 Patients must be able to swallow capsules

3.1.4 Age:

Patients must be ≥ 3 years to ≤ 45 years of age at start of treatment

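### Section 5.4.3 carries two loperamide schedules that disagree: weight-banded Table 6, and a diarrhea algorithm with no weight or age condition visible

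*Combined protocol and SAP*

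**What the plan says.** Section 5.4.3 (Diarrhea) tells staff to use the Table 6 loperamide guidelines when diarrhea occurs. Table 6 is titled "Weight Specific Guidelines for Therapeutic Use of Loperamide". Its columns are weight in kg, initial dose in mg, later daytime dose and later night-time dose. Three of its rows read "10-20 1 1mg q 3h 1mg q 4h", "20-30 2 1mg q 3h 2mg q 4h" and "30-42 2 1mg q 2h 2mg q4h". Below them is an 8-10 kg row, also with a 1 mg initial dose. Above them is a row for more than 42 kg: 4 mg initially, 2 mg every 2 hours by day and 4 mg every 4 hours by night.

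Directly after the table, the same section refers the reader to an algorithm for assessing diarrhea. Its loperamide box reads "Loperamide : 4mg initially" and "then 2mg every 4 hours or after each unformed stool". The algorithm separates uncomplicated grade 1-2 diarrhea from complicated or grade 3-4 diarrhea. The loperamide box appears to belong to the uncomplicated branch; the other branch refers to hospitalization and local practice.

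The diarrhea row of Table 7 (Section 6.2) applies when anti-diarrheal treatment is ineffective, and it sends the reader back to both the algorithm and the guidelines. On age, Section 3.1.4 says "Patients must be ≥ 3 years to ≤ 45 years of age at start of treatment". Section 5.1 advises against selumetinib below a body surface area (BSA) of 0.55 m².

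**The concern.** Both schedules are current protocol text for the same event, and nothing says which one governs. Table 6 varies with weight; the readable algorithm does not. A child in a lower weight band therefore has two different prescribed doses, and staff working from the algorithm could give more than Table 6 gives.

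The event will not be rare. Section 7 lists diarrhea among the adverse events expected in at least 20% of patients.

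There is also a knock-on effect for the study drug. Table 7 makes action on selumetinib depend on whether anti-diarrheal treatment has failed. With two regimens in force, that judgement could differ according to which was used, so holds and reductions for diarrhea could be applied inconsistently.

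**Working it through.** The documents state no figure to reproduce here. The check sets the two schedules side by side. All dose inputs come from Section 5.4.3.

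**Initial dose.** Ratio = algorithm initial dose / Table 6 initial dose.

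- 8-10 kg and 10-20 kg: 4/1 = 4.0
- 20-30 kg and 30-42 kg: 4/2 = 2.0
- Above 42 kg: 4/4 = 1.0

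**Follow-on rate.** The algorithm gives 2 mg / 4 h = 0.50 mg/h, leaving out stool-triggered doses. Table 6 gives:

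| Weight (kg) | Day (mg/h) | Algorithm / Table 6, day | Night (mg/h) | Algorithm / Table 6, night |
|---|---|---|---|---|
| 10-20 | 1/3 = 0.33 | 1.5 | 1/4 = 0.25 | 2.0 |
| 20-30 | 1/3 = 0.33 | 1.5 | 2/4 = 0.50 | 1.0 |
| 30-42 | 1/2 = 0.50 | 1.0 | 2/4 = 0.50 | 1.0 |
| >42 | 2/2 = 1.00 | 0.5 | 4/4 = 1.00 | 0.5 |

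**Scheduled first-day total.** The protocol does not define day and night, so 16 daytime and 8 night-time hours are assumed. Total = initial dose + (16 / day interval) × day dose + (8 / night interval) × night dose.

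- Algorithm: 4 + (24/4) × 2 = 16 mg at any weight
- Table 6, 10-20 kg: 1 + (16/3) × 1 + (8/4) × 1 = 8.3 mg; 16/8.3 = 1.9
- Table 6, 20-30 kg: 2 + (16/3) × 1 + (8/4) × 2 = 11.3 mg; 16/11.3 = 1.4
- Table 6, 30-42 kg: 2 + (16/2) × 1 + (8/4) × 2 = 14 mg; 16/14 = 1.1
- Table 6, above 42 kg: 4 + (16/2) × 2 + (8/4) × 4 = 28 mg; 16/28 = 0.57

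Stool-triggered dosing could raise the algorithm total. The documents give no stool frequency, so that part is not quantified.

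**Can an enrolled child fall in a 1 mg row?** The documents give no weights, so two assumptions are needed: the Mosteller formula, BSA = √(height × weight / 3600), and heights of 90 to 105 cm. Rearranged, weight = BSA² × 3600 / height.

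- BSA 0.55 m²: 0.3025 × 3600 / 105 = 10.4 kg, up to 0.3025 × 3600 / 90 = 12.1 kg
- BSA 0.69 m²: 0.4761 × 3600 / 105 = 16.3 kg, up to 0.4761 × 3600 / 90 = 19.0 kg

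The lowest row of the selumetinib dosing table (0.55-0.69 m²) therefore falls in the 10-20 kg band. A 10 kg child at 0.55 m² would need a height of 0.3025 × 3600 / 10 = 109 cm, outside the assumed range. The 8-10 kg row is thus barely reachable, and the comparison starts at 10 kg.

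**The case against.** **The text gives a reading order.** The one sentence that directs loperamide dosing points to Table 6, while the algorithm is introduced for assessment. This softens the conflict. It does not remove it, because the algorithm carries its own dose and interval, is invoked without limit, and is cited again beside the guidelines in Table 7.

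**The algorithm may be meant for adults.** That is possible. The figure was flattened on extraction and some of its text seems to be missing, so a qualifier could have been lost. What can be said is that none is visible. Section 5.4.4, by contrast, marks its adult rash steps explicitly. This caveat stands and should be checked against the original figure.

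**Stronger readings the documents do not support.** A reader might infer that every patient with diarrhea is assigned 4 mg. The branch structure points against that, since the loperamide box appears to cover only uncomplicated grade 1-2 diarrhea. A reader might also infer that small children would receive four times the Table 6 amount overall. The fourfold ratio concerns the single initial dose; the scheduled first-day ratio at 10-20 kg is 1.9. Nor do the documents show that staff would follow the algorithm over the table, only that they could.

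**The number affected may be small.** Patients must be able to swallow capsules, and this is one children's hospital. Both points limit the exposure, but neither settles which instruction applies.

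**Conclusion.** The contradiction holds. Within one section, the two loperamide schedules differ in every weight band from 10 kg up. The gap in initial dose is fourfold at 10-20 kg, twofold at 20-42 kg and nil above 42 kg. The gap in scheduled first-day total runs from 1.9-fold at 10-20 kg to 1.1-fold at 30-42 kg, and reverses above 42 kg, where the algorithm gives 0.57 of the Table 6 total. Because the direction changes, neither schedule can be read as a cautious version of the other.

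The initial-dose ratios come straight from the text. The first-day totals rest on the assumed 16/8 hour split and leave out stool-triggered doses. The claim that enrolled children reach a 1 mg row rests on the assumed formula and heights. The absence of a weight or age condition is a statement about the readable text only.

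This is a patient-safety inconsistency in supportive care, with a possible effect on how Table 7 is applied. It does not touch the endpoints, the two-stage design or its error rates. No view is taken on which schedule is right.

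**What to change.** The sponsor should check the original figure, then do one of two things:

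- reconcile the algorithm with Table 6, so that a single loperamide instruction applies at each weight; or
- label the algorithm with the age or weight group it is meant for, and state in Section 5.4.3 which source prevails.

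The diarrhea row of Table 7 should then point to that one instruction, so that treatment failure is judged against the same regimen in every patient. The choice of dose is for the sponsor's clinical team, and none is proposed here.

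The cost is a wording change and a corrected figure. Sample size, visit schedule and analysis do not change.
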